#### **11.3.5 Hospital Anxiety and Depression Scale**

The mean Anxiety and Depression scores for the HADS and mean changes from baseline will be summarized by IBS subtype (including combined), treatment group, and visit. P-values from t-tests comparing mean change from baseline between Blautix and placebo will be presented at each post-baseline visit for exploratory purposes. Means for subscales with questions missing responses will not be calculated.

All response data from the HADS and the derived Anxiety and Depression scores will be listed.

### **11.4 Exploratory Analyses**

CCI

## **12. SAFETY ANALYSES**

All safety analyses will be based on the safety set. For summaries of laboratory values and vital signs by visit, unscheduled visits will not be presented. To capture all potential safety signals, the maximum and minimum values observed at any time during the study (including unscheduled visits) will be presented in addition to scheduled timepoints.

### **12.1 Extent of Exposure**

The first and last dates of study drug administration are collected in the eCRF. The duration of treatment in days will be calculated as Last Dose Date - First Dose Date + 1.

Actual dosing is collected in the eCOA device as whether morning dose was taken and whether evening dose was taken. This data will be used to compute total capsules taken (2 per dose) and compliance.

Calculation of compliance requires an expected number of capsules taken. Subjects may have taken only the evening dose on the day of the Baseline (Day 1) visit. Likewise, only the morning dose may have been taken on the last day of dosing. As an approximation to the expected number of capsules taken, 4 times the duration of treatment in days minus 1 will be used. That is, compliance as a percent will be calculated as:

$$100 \times (2 \times (\text{Sum of doses taken from eCOA})) / (4 \times (\text{Duration of treatment} - 1))$$

Study drug exposure will be summarized by IBS subtype (including combined) and treatment group for each treatment using the duration of treatment and the total number of capsules taken.

Study drug compliance will be summarized using frequencies and percentages as categorized below:

- >110%
- >90%-110%
- >80%-90%
- >70%-80%
- <=70%

## 12.2 Adverse Events

All AE summaries will be restricted to treatment-emergent AEs (TEAEs), which are defined as those AEs that occurred or worsened on or after the first day of dosing. Reported AEs should also include existing AEs that worsened during the study. If it cannot be determined whether the AE is treatment emergent due to a partial onset date, then it will be counted as such. Verbatim terms in the eCRFs will be mapped to preferred terms and system organ classes using MedDRA.

Each AE summary will be displayed by IBS subtype (including combined) and treatment group. Summaries that are displayed by system organ class and preferred terms will be ordered by descending order of incidence of system organ class and preferred term within each system organ class as observed in all subjects. Ties will be broken alphabetically. Summaries of the following types will be presented:

- Overall summary of TEAEs that contain an overview of each item below.
- Subject incidence of TEAEs and total number of unique TEAEs by MedDRA system organ class and preferred term.
- Subject incidence of TEAEs by MedDRA system organ class, preferred term, and highest severity. At each level of subject summarization, a subject is classified according to the highest severity if the subject reported 1 or more events. Adverse events with missing severity will be considered severe for this summary.
- Subject incidence of TEAEs by MedDRA system organ class, preferred term, and closest relationship to study drug (Possibly Related/Not Possibly Related). At each level of subject summarization, if a subject reported 1 or more events, a possibly related TEAE will be counted over a not possibly related TEAE. Adverse events with a missing relationship will be considered related for this summary.
- Subject incidence of serious TEAEs and total number of unique serious TEAEs by MedDRA system organ class and preferred term.

- Subject incidence of TEAEs leading to death as an outcome by MedDRA system organ class and preferred term.
- Subject incidence of TEAEs leading to study discontinuation by MedDRA system organ class and preferred term.

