6.7 Permitted Dose Adjustments and Interruptions

No dose adjustments or interruptions will be permitted. Treatment should be withdrawn in subjects who are unable to tolerate it.

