8.2 Definitions

8.2.1 Adverse Events

An adverse event is any untoward medical occurrence in a subject administered study medication and which does not necessarily have to have a causal relationship with this treatment. Abnormal laboratory values or test results constitute adverse events only if they induce clinical signs or symptoms, are considered clinically significant, or require therapy.

The occurrence of adverse events should be sought by non-direct questioning of the subject at baseline (pre-dose) Adverse events will be checked at every clinic visit. Adverse events may be detected when they are volunteered by the subject or through physical examination, laboratory test, or other assessments. All adverse events must be recorded in the CRF with the following information:

- 1. Diagnosis: diagnosis if known, otherwise sign or symptom;
- 2. Seriousness: whether it constitutes a serious adverse event (SAE) and therefore requires reporting immediately (see Section 8.3)
- 3. Criteria for Adverse Events:

Mild: Asymptomatic or mild symptoms; clinical or diagnostic observations only; intervention not indicated

Moderate: Moderate; minimal, local or non-invasive intervention indicated; limiting ageappropriate instrumental ADL (Activities of Daily Living)

Severe: Severe or medically significant but not immediately life-threatening; hospitalization or prolongation of existing hospitalization indicated; limiting self-care ADL (Activities of Daily Living)

- 4. Relatedness: relationship to the study medication will be assessed as reasonable possibility of being related or no reasonable possibility of being related;
- 5. Duration: start and end dates or, if continuing, at final examination;
- 6. Action: any action taken to manage it (none, dosing interrupted, dosing stopped, other, medication);

7. Outcome: the outcome (completely recovered, recovered with sequelae, condition improving, condition still present and unchanged, condition deteriorated, death).

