8.2.2 Serious Adverse Events

A serious adverse event is defined as an event which:

- results in death
- is life-threatening
- requires hospitalisation or prolongation of hospitalisation
- results in persistent or significant disability or incapacity
- consists of a congenital anomaly or birth defect
- is a medically important event

All adverse events should be treated appropriately. Treatment may include one or more of the following: no action taken (i.e., further observation only); study medication discontinued due to this adverse event; concomitant medication given; non-drug therapy given. The action taken to treat the adverse event or resolve the adverse incident should be recorded on the CRF.

Once an adverse event is detected, it should be followed until its resolution. The suspected relationship to the study medication, the interventions required to treat it and the outcome must be recorded in the CRF.

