8.4 Clinical Management of Events

If a subject chooses to withdraw or is withdrawn, the Investigator must ensure the safety and wellbeing of the subject prior to final discharge from the study. All adverse events will be evaluated, treated and followed up. Repeated and unscheduled examinations and laboratory assessments should be conducted as needed until appropriate and satisfactory resolution of any abnormalities.

Every effort should be made for all randomised subjects to undergo final follow-up. In the event that a subject fails to return for the study visits and follow-up assessments, every effort should be made to determine the reason(s).

Any pregnancy will be followed up by the investigator to determine outcome for the mother and baby.

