# 9. STUDY POPULATION

## 9.1 Subject Disposition

Subject disposition information will be summarized for all subjects by IBS subtype and treatment group. Summary columns will also be included for subtype and overall totals. Summaries will include: the number of subjects screened and the number of screen failures, the number of subjects randomised, the number and percentage of subjects in each analysis set, the number and percentage of subjects completing the study, and the primary reason for discontinuation. The number of subjects randomised will be the denominator for percentages.

A separate summary will show the reasons for screen failure with percentage of subjects who failed screening for each reason. The reasons for screen failure will also be listed.

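### SAP 12.2 summarises adverse events leading to study discontinuation but not those leading to discontinuation of study drug, although the protocol has drug stopping recorded for each event

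*SAP*

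**What the plan says.** **SAP.** Section 12.2 lists seven TEAE summaries. One concerns stopping: "Subject incidence of TEAEs leading to study discontinuation by MedDRA system organ class and preferred term". The overall table is described as "Overall summary of TEAEs that contain an overview of each item below", so it brings in nothing beyond the listed items. SAP 9.1 plans "the number and percentage of subjects completing the study, and the primary reason for discontinuation" and no separate account of treatment completion.

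**Protocol.** Section 6.7 says: "Treatment should be withdrawn in subjects who are unable to tolerate it". Section 8.2.1 requires, for each adverse event, "any action taken to manage it (none, dosing interrupted, dosing stopped, other, medication" and so on. Section 8.2.2, in a paragraph covering all adverse events, lists "study medication discontinued due to this adverse event" as a possible action and has the action taken entered on the CRF. Section 8.4 adds: "Every effort should be made for all randomised subjects to undergo final follow-up".

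**The concern.** The protocol has an item that says directly whether an adverse event ended dosing, and no planned summary uses it. The SAP summarises a different event, leaving the study. The two agree only if every subject who stops capsules because of an adverse event is also recorded as having discontinued the study.

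Safety of the repeated dose is the trial's only secondary objective. With a fixed dose and no adjustments permitted, stopping the drug because of an adverse event is the most direct measure of tolerability. If the two events differ, the planned table understates it by an amount that depends on how sites classify subjects.

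**Working it through.** The documents state no figure on this point, so the check is mainly a comparison of texts.

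**Step 1. Does stopping the drug always mean leaving the study?**

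- *Stopping drug, with no mention of leaving:* Protocol 6.7 (treatment withdrawn for intolerance), 8.2.1 and 8.2.2 (action taken). Protocol 8.3 asks SAE follow-up reports to say whether the subject stayed in the study or left, so staying after an SAE is foreseen.
- *Leaving the study for safety:* Protocol 4.2.2.1, the safety item among the reasons for withdrawal in 5.4.1, and 5.4.2 (no replacement of subjects withdrawn for adverse events). Section 8.3.1 pairs stopping medication with withdrawal from the study, but for pregnancy.
- *Both:* Protocol 5.4.1 gives one list of reasons for removal from product or from assessments, without defining separate statuses.

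No passage sets out an off-drug, on-study pathway, and no passage rules one out. None says that a drug stop must be recorded as study discontinuation.

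**Step 2. Would another planned output show a subject who is off drug for an adverse event but not recorded as discontinued from the study?**

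| SAP output | What it shows |
|---|---|
| 12.2 TEAE incidence, severity, relatedness | The event, not that dosing stopped |
| 12.2 TEAEs leading to study discontinuation | Nothing for this subject |
| 9.1 disposition | Study completion and a discontinuation reason; treatment status not separated |
| 12.1 treatment duration | A short duration, not linked to an event or reason |
| 12.1 compliance | See step 3 |
| 8 Efficacy Evaluable Set | Completion of the 8 weeks is defined by a visit between days 49 and 64, which is attendance, not dosing |
| 6 data listings | eCRF data subject by subject, not compared between arms |

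**Step 3. Compliance.** SAP 12.1 gives compliance = 100 × (2 × doses taken) / (4 × (duration − 1)), where duration runs from first to last dose. For a subject whose last dose is on day 14:

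- all 28 doses taken: 100 × (2 × 28) / (4 × 13) = 100 × 56/52 = 107.7%;
- 26 doses taken: 100 × (2 × 26) / (4 × 13) = 100 × 52/52 = 100%.

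Both fall in the >90%–110% category. The denominator ends at the last dose, so early stopping does not lower compliance.

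**Step 4. Size.** Let *a* be the proportion stopping drug for an adverse event and *b* the share of those not recorded as study discontinuations. Missed subjects per arm = 125 × *a* × *b*. The documents give neither value. Purely as an assumption, *a* = 3% to 8% gives 3.75 to 10 such subjects per arm. The number missed is then 0 if *b* = 0, about 2 to 5 if *b* = 0.5, and at most 3.75 to 10 if *b* = 1. This illustrates the dependence on *b* and is not an estimate.

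**The case against.** The strongest reply is that stopping for an adverse event may in practice mean leaving the study. Protocol 4.2.2.1, 5.4.1 and 5.4.2 all describe withdrawal from the study on safety grounds, and SAP 9.2 names as a possible major deviation a subject who developed withdrawal criteria but was not withdrawn. Where sites work this way, the existing table counts these subjects. The TEAEs themselves also remain in the general tables, treatment duration is summarised by arm, and eCRF data are listed. The discontinuation reason in SAP 9.1 is not expressly limited to study discontinuation. The table specifications sit in a separate file (SAP Appendix C), which may already contain the missing table.

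Most of this stands, and it rules out stronger readings that a reader might infer:

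- *That the protocol withdraws the treatment and keeps the subject.* Protocol 6.7 names treatment only. It does not say that the subject stays.
- *That a subject who stops early and attends follow-up counts as a completer, so that better retention makes the table worse.* Protocol 5.4.1 asks subjects who withdraw after dosing starts to undergo the follow-up assessments, and the 8.4 sentence on final follow-up comes after text on withdrawn subjects. Attendance therefore does not establish completion. The narrative in Protocol 4.2.1 times follow-up 4 to 6 weeks after the last dose, so a subject stopping at the end of week 2 would be due around weeks 6 to 8.
- *That a particular number of subjects will be missed, or that their data are lost.* The documents support neither.

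What the reply does not supply is a rule making every drug stop for an adverse event a recorded study discontinuation, or a planned between-arm summary that works without one.

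**Conclusion.** The point holds as a gap in the safety summaries. SAP 12.2 counts adverse events that end study participation, but not those that end dosing, although the protocol has the latter recorded. Subjects off drug and still on study, if there are any, would be visible individually but absent from every between-arm summary of stopping for an adverse event. How many there would be cannot be derived.

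The conclusion assumes that the separate table specifications do not already contain such a summary; the SAP text does not call for one. The primary analysis, alpha and power are untouched. The change should be made because it removes the dependence on site classification at almost no cost, not because a large error has been shown.

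**What to change.** 1. **SAP 12.2.** Add subject incidence of TEAEs with action taken 'dosing stopped', by system organ class and preferred term, with a line in the overall summary. Keep the study-discontinuation table beside it, and state what study discontinuation covers.
2. **SAP 9.1.** Report completion of treatment and the reason for stopping it separately from completion of the study, to the extent that the eCRF collects this.
3. **Interruptions.** Protocol 6.7 says "No dose adjustments or interruptions will be permitted", while 8.2.1 offers 'dosing interrupted' as a recordable action. These passages must be reconciled. Any row for interruptions would be descriptive only.

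The cost is SAP wording, one added table and a few rows, settled before database lock. No new data are needed for item 1 if the eCRF carries the action-taken item as the protocol requires.

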### **12.3 Clinical Laboratory Evaluation**

Laboratory parameters (serum chemistry and hematology) will be summarized using descriptive statistics at baseline, at each postbaseline time point, and for the minimum and maximum values observed (including unscheduled visits). Changes from baseline will also be summarized.

In addition, shift tables (i.e., low-normal-high at baseline versus low-normal-high at follow-up in a 3-by-3 contingency table) will be provided to assess changes in laboratory values from baseline to follow-up.

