Subjects will receive further study medication to last until the next clinic visit. Subjects will be reminded to take their medication; two (2) capsules to be taken at 12 hourly intervals approximately 30 minutes before meals. Subjects will receive a total of four (4) capsules per day and will be reminded to store the capsules in the fridge and not to open the capsules.

Subjects will be provided with a kit with instructions for the collection of a stool sample. They will be asked to provide a stool sample from the night before or on the morning of the next clinic visit

End of Treatment (Week 8)

Subjects will return to the clinic at the end of the 8-week (or up to -7 days) treatment period. Subjects will be assessed (vital signs, concomitant medication and adverse events) and a physical examination, including weight and BMI and an ECG will be conducted. A urine pregnancy test for female subjects of child bearing potential. Bloods for haematology, serum biochemistry and inflammatory markers will be taken. A fresh urine sample will be taken to analyse the metabolites.

Subjects will continue to use their smartphones to capture all the patient related outcome data, except for IBS-SSS and FFQ questionnaires which will be completed during the clinic visit on a table device. The data will be reviewed on an ongoing basis as required by the study team and sponsor. At this visit the following information will be reviewed with the subject;

- Information on Adverse Events
- Review of Medication log completed daily
- Abdominal Pain Score completed daily
- Stool consistency/frequency and laxative use daily
- Subject Global Assessment of Relief completed weekly
- IBS Quality of Life questionnaire (IBS QOL) on the Day of Clinic Visit or within 24 hours prior to the visit
- IBS Symptom Severity Score (IBS-SSS) on the Day of Clinic visit
- Hospital Anxiety and Depression score (HADS) on Day of Clinic visit or within 24 hours prior to the visit
- Food Frequency Questionnaire (FFQ) on the Day of Clinic visit
- Review of concomitant medications

Subjects will be provided with a kit with instructions for the collection of a stool sample. They will be asked to provide a stool sample from the night before or on the morning of the next clinic visit

Follow-Up (Week 12-14)

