Subjects will return 4-6 weeks after the last dose of study medication for a safety check and clinical update. All female subjects of child bearing potential will have a urine pregnancy test. A physical examination, weight and vital signs will be measured and recorded, changes in concomitant medication and adverse events will be recorded. Bloods will be drawn for haematology, serum biochemistry

Subjects will use their smartphone issued to capture their study related data, except for IBS-SSS and FFQ questionnaires which will be completed during the clinic visit on a tablet device.

- Information on Adverse Events
- Abdominal Pain Score completed daily
- Stool consistency/frequency and laxative use, daily
- Subject Global Assessment of Relief completed weekly
- IBS Quality of Life questionnaire (IBS QOL) on the Day of Clinic Visit or within 24 hours prior to the visit
- IBS Symptom Severity Score (IBS-SSS) on the Day of Clinic visit
- Hospital Anxiety and Depression score (HADS) on Day of Clinic visit or within 24 hours prior to the visit
- Food Frequency Questionnaire (FFQ) on the Day of Clinic visit
- Review of concomitant medications

At this visit the smartphones will be returned from the subjects and given back to the study site team.

Summary of Assessments

Details of the study assessments and other procedures to be performed are presented in Table 1 and in Section 7, Study Assessments.

TABLE 2: SCHEDULE OF ASSESSMENTS AND PROCEDURES

	Screening Visit (Day-28 to Day-1)	Baseline Visit 1 (Day 1) Week 1	Visit 2: Week 4 (±7 days)	End of Treatment Week 8 (-7 days)	Follow-Up: Week 12- 14
General Assessments					
Informed Consent (prior to any screening procedures)	X				
Inclusion/Exclusion	X	X			
Medical history/demographics	X				
Physical examination	X	X		Х	X
Vital signs	X	X		Х	X
Weight/Height/BMI	X	X ^e		X ^e	X ^e
ECG	X			Х	
Concomitant medication	X	X	Х	Х	X
Adverse Event Recording ^a	X	X	Х	Х	X
Randomisation (8 Week Treatment Period)					
Study Drug		X	Х		
Dosing Diary ^b		X	х		
Laboratory Assessments					
Blood samples (haematology and clinical chemistry)	X			Х	X
Blood sample (viral serology)	X				
CCI		X	Х	Х	X
Stool sample		X	х	Х	X
CCI		X	х	Х	X

Pregnancy test ^c	Х	X	Х	Х	х
Clinical Outcome Assessments - eCOA					
Abdominal Pain score ^d	Х	X	Х	Х	х
Stool frequency and consistency score ^d	Х	X	Х	Х	х
Food Frequency Questionnaire		X	Х	Х	Х
Subject Global Assessment of Relief		X	Х	Х	Х
IBS Quality of Life (QOL)		X	Х	Х	х

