#### 4. STUDY DESIGN AND PLAN

This is a randomised, placebo-controlled, parallel group, repeat dose multicentre study in adult male and female subjects of 18 to 70 years of age with a confirmed diagnosis of IBS-C or IBS-D.

The study consists of a Screening Visit, a Baseline Visit (Day 1), an 8-week treatment period with 2 clinic visits, Visit 2 (Week 4) and End of Treatment (Week 8), and a Follow-up Visit 4-6 weeks after the last dose of study medication for a safety check and clinical update.

The Screening Visit is up to 4 weeks before dosing starts. Subjects who fulfill all the eligibility criteria will be provided with an electronic device containing an Electronic Clinical Outcomes Assessment (eCOA) App and will be provided with training and instructions on how to use the device. At this visit, they will complete the IBS-Symptom Severity Score (IBS-SSS) on a device during the clinic visit.

The subjects will be asked to take the device home and complete the following assessments daily over a minimum of a 7-day period prior to attending the clinic for their Baseline Visit 1:

- An abdominal pain intensity rating scale daily
- Bowel movements, Stool consistency/frequency daily and laxative use; if no bowel movements, this should be recorded as zero

The subjects will need to ensure they complete these two assessments at least one day prior to the day of the next clinic visit. The same device will be used throughout the study for all patient reported outcome assessments.

Each subject will be provided with a kit with instructions for the collection of a stool sample. They will be asked to provide a stool sample from the night before or on the morning of the next clinic visit. If necessary, a stool sample may be provided up to 2 days after the Baseline visit provided it is from the night before or from the day it is delivered to the clinic.

At the Baseline visit, the study doctor will review the screening data obtained from the device eCOA app and the subject will be classified into either IBS-C or IBS-D subtypes. Subjects will be randomised to receive either Blautix™ or placebo capsules, with instructions for two (2) capsules to be taken at approximately 12-hour intervals; morning and evening, approximately 30 minutes before meals, giving a total of four (4) capsules per day.

Specific assessments performed at each visit are tabulated in the following Schedule of Assessments and Procedures.

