| Randomisation (8 Week Treatment Period)       |                                      |                                       |                                       |  |                              |
| Study Drug   |                                      | x                                     | x                                     |  |                              |
| Dosing Diary b                            |                                      | x                                     | x                                     |  |                              |
| Laboratory Assessments                        |                                      |                                       |                                       |  |                              |
| Blood samples (haematology and clinical chemistry)   | x                                    |                                       |                                       | x  | x                            |
| Blood sample (viral serology)                        | x                                    |                                       |                                       |  |                              |
| CCI [REDACTED]                                       |                                      | x                                     | x                                     | x  | x                            |
| Stool sample   |                                      | x                                     | x                                     | x  | x                            |
| CCI [REDACTED]                                       |                                      | x                                     | x                                     | x  | x                            |

|  |   |   |   |   |   |
|--|---|---|---|---|---|
| Pregnancy test c                        | x | x | x | x | x |
| Clinical Outcome Assessments - eCOA         |   |   |   |   |   |
| Abdominal Pain score d                  | x | x | x | x | x |
| Stool frequency and consistency score d | x | x | x | x | x |
| Food Frequency Questionnaire                       |   | x | x | x | x |
| Subject Global Assessment of Relief                |   | x | x | x | x |
| IBS Quality of Life (QOL)                          |   | x | x | x | x |
| IBS-Symptom Severity Score (SSS)                   | x | x | x | x | x |

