### **12.6 Electrocardiogram**

Overall interpretation results for ECG will be summarized using shift tables (Normal, Abnormal Not Clinically Significant, Abnormal Clinically Significant) comparing baseline to Week 8.

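### The laboratory shift tables run only from baseline to the off-drug follow-up visit, so changes of category at End of Treatment (Week 8) are not shown in the shift tables

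*SAP*

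**What the plan says.** SAP 12.3 plans two kinds of laboratory output. The first is descriptive statistics at baseline, "at each postbaseline time point, and for the minimum and maximum values observed (including unscheduled visits", with changes from baseline. The second is "shift tables (i.e., low-normal-high at baseline versus low-normal-high at follow-up in a 3-by-3 contingency table", whose stated purpose is "to assess changes in laboratory values from baseline to follow-up".

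SAP section 4 describes "a Follow-up Visit 4-6 weeks after the last dose of study medication for a safety check and clinical update". Protocol 4.2.1 agrees: "Subjects will return 4-6 weeks after the last dose of study medication for a safety check and clinical update". In both schedules of assessments this visit has its own column, Week 12-14.

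The schedule row "Blood samples (haematology and clinical chemistry" is marked at Screening, End of Treatment and Follow-Up, with nothing at Day 1 or Week 4. For the End of Treatment visit, Protocol 4.2.1 states: "Bloods for haematology, serum biochemistry and inflammatory markers will be taken".

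**The concern.** Haematology and blood chemistry are a named safety endpoint (Protocol 3.2), and safety is the secondary objective. A shift table is the usual way to see how many subjects in each arm left the normal range. Here the only shift table named uses a sample taken some weeks after dosing stopped, while the sample taken at the end of dosing has none.

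An effect on a laboratory value that reverses off drug could therefore be present at Week 8 and leave the shift tables clean. What is at stake is a count by arm at the visit most informative about exposure. No test, confidence interval or sample size is affected.

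**Working it through.** The plan states no figure on this point, so the check compares the text with the visit schedule.

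**1. Which visit follow-up means.** End of dosing is Week 8. Week 8 + 4 weeks = Week 12, and Week 8 + 6 weeks = Week 14, which matches the Week 12-14 column. Three things in the SAP support reading the lower-case word in 12.3 as this visit:

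- Section 11.2 uses lower-case follow-up twice, once alongside the treatment period and once to say that it is left out of the treatment-period model. Both uses mean the time after treatment.
- Section 12.3 itself has a phrase for all visits after baseline and uses it for the descriptive statistics. It then changes to follow-up for the shift tables.
- Section 12.3 repeats follow-up when it gives the purpose of the tables, so the word is not a single slip.

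**2. What each scheduled post-baseline sample receives.**

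| Sample | Descriptive statistics and change | Minimum/maximum | Subject listing | Shift table |
|---|---|---|---|---|
| End of Treatment, Week 8 | yes (12.3) | yes (12, 12.3) | yes (6) | none named |
| Follow-Up, Week 12-14 | yes (12.3) | yes (12, 12.3) | yes (6) | yes (12.3) |

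One of the two scheduled post-baseline samples has no shift table, and it is the on-treatment one.

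**3. What the planned table can distinguish.** Take a subject who is normal at baseline and consider one upper limit:

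| Week 8 | Follow-up | Cell in the planned table |
|---|---|---|
| normal | normal | normal to normal |
| high | normal | normal to normal |
| normal | high | normal to high |
| high | high | normal to high |

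The four patterns fall into two cells. A rise at Week 8 that has resolved cannot be told from no change. A rise that first appears off drug cannot be told from one already present at Week 8.

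**4. Whether another output supplies the count.**

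- Descriptive statistics at Week 8 describe the distribution. They do not count subjects who crossed a limit relative to their own baseline.
- The minimum and maximum are taken over the whole study, so they are not specific to Week 8, and they are not classified against normal limits.
- Listings hold the individual values but do not tabulate them by arm.
- Adverse event tables (SAP 12.2) count subjects by arm. Protocol 8.2.1, however, makes an abnormal value an adverse event only if it causes signs or symptoms, is judged clinically significant or needs therapy.

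What remains uncounted is a crossing of a normal limit at Week 8 that is asymptomatic, not judged clinically significant and resolved by follow-up.

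**5. What baseline means here.** No laboratory sample is scheduled on Day 1, and SAP 10.2 defines baseline for efficacy assessments only. The laboratory baseline must therefore be the screening sample, which 12.3 does not say.

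**The case against.** The strongest reply is that little is hidden. Week 8 values are summarised, contribute to the minimum and maximum, and are listed by subject. Abnormalities that matter clinically are counted by arm as adverse events. All of this stands, and it limits the point to the shift tables. A reader might infer that end-of-treatment abnormalities go unreported altogether; the documents do not support that.

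Second, follow-up might be meant loosely as any visit after baseline. The table specifications (v2.0, cited in SAP Appendix C) are a separate document that was not available for this review and may already include a Week 8 shift. That possibility is open. The SAP's own usage points the other way, and if the specifications do cover Week 8, the text of 12.3 should be brought into line.

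Third, Protocol 5.4.1 asks that subjects who stop early have, where possible, the assessments of the follow-up visit. Their follow-up sample may lie closer to exposure than Week 12-14. This also stands: it would be too strong to say that the table describes recovery only. It does not help subjects who complete treatment, whose follow-up sample is off drug by design.

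A reader might also see an inconsistency with SAP 12.6, where the ECG shift is drawn up by "comparing baseline to Week 8". That comparison carries no weight. ECGs are scheduled only at Screening and End of Treatment, so Week 8 was the only choice available.

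**Conclusion.** The point holds for the shift tables and no further. As written, SAP 12.3 gives no count by arm of subjects who move from normal to low or high at Week 8, the only scheduled on-treatment haematology and chemistry sample. No other planned output supplies that count for abnormalities that fall short of an adverse event.

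The conclusion rests on reading follow-up as the named visit, which the SAP's usage supports, and on the table specifications not already adding Week 8. The number of subjects affected cannot be estimated: the documents give neither a rate of laboratory abnormality nor a rate of recovery, and any figure would only restate what was assumed. The laboratory analyses are descriptive, so no inference changes. This should be corrected, but it does not threaten the trial's main conclusions.

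**What to change.** In SAP 12.3, state that:

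- laboratory baseline is the screening sample;
- shift tables will be produced, by subtype and arm, from baseline to End of Treatment (Week 8);
- shift tables will also be produced from baseline to the worst post-baseline value, including unscheduled and early-withdrawal samples. Because a value can be abnormal in either direction, this means one table for the lowest value and one for the highest;
- the baseline-to-Follow-Up table is kept and labelled as the recovery table.

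The table specifications should be checked and made to match. The cost is a few sentences of SAP text and extra runs of the same table program on data already collected, with somewhat more output to review. No visit, sample or clinical procedure changes.
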